## 12. Statistical Considerations

### 12.1. Number of Participants

Forty evaluable neonates: Stage 1, two sequential cohorts - Cohort 1A (n=8) and Cohort 1B (n=8); Stage 2, Cohort 2 (n=24).

One of the primary objectives of this study is to assess the pharmacokinetics of DTG following administration of 5 mg (half of the 10 mg DTG-DT). In each cohort, we aim to achieve at least 80% power to obtain a 95% CI for DTG CL/F that lies within 60% and 140% of the geometric mean estimate of DTG CL/F in a prior relevant study, per FDA guidance for paediatric PK studies (2). In children in the lowest weight band (3 to <6 kg) of the ODYSSEY trial, DTG CL/F geometric coefficient of variation (CV%) with the 5 mg dispersible DTG tablet was 33%. In neonates, the variability is expected to be higher, with CV% within the range of 30% to 50%. Conservatively assuming that, in each cohort, CV% will be 50%, a sample size of 8 evaluable neonates in Cohort 1A, 8 in Cohort 1B and 24 in Cohort 2 will achieve 86%, 86% and >99% power, respectively, to obtain a 95% CI that lies within 60% and 140% of the geometric mean estimate. These power calculations are based on the Student's t-distribution and apply the methodology described by Wang et al. for rich PK sampling (3).

The other primary objective of this study is to evaluate the safety of DTG in neonates. This will be assessed through proportions of participants with events, such as AEs of Grade 3 or higher.

**Table 10** provides binomial probabilities of having at least one subject with an event for a range of sample sizes and true proportions of participants with an event. For example, if the true proportion of participants experiencing an AE of Grade 3 or higher is 5%, the probability of having at least one participant experiencing an AE of Grade 3 or higher out of 40 participants is 0.87.

**Table 10.** Binomial probabilities of having at least one participant with an event for a range of sample sizes and true proportions of participants with an event.

True proportion of participants with an event	Sample Size			
	N=8	N=16	N=24	N=40
1%	0.08	0.15	0.21	0.33
2%	0.15	0.28	0.38	0.55
3%	0.22	0.39	0.52	0.70
4%	0.28	0.48	0.62	0.80
5%	0.34	0.56	0.71	0.87
6%	0.39	0.63	0.77	0.92
7%	0.44	0.69	0.82	0.95
8%	0.49	0.74	0.86	0.96
9%	0.53	0.78	0.90	0.98
10%	0.57	0.81	0.92	0.99

The precision of the observed proportions of participants with an event will be measured using 95% Clopper-Pearson confidence intervals (CI). For example, if 3 (8%) out of 40 participants experience an AE of Grade 3 or higher, the 95% CI would be 2% to 20%.

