### 8.2.1. Dolutegravir Dosing in Neonates

**No specific DTG dosing guidelines are available for neonates.** Based on the WHO weight band dosing guidelines the DTG dose range is between 0.85 to 1.67 mg/kg for children >4 weeks and weighing between 3 and 5.9 kg. In Cohort 1A, 5 mg of DTG, i.e., half of the scored 10 mg DTG-DT, will be administered to neonates who are ≥14 days and <28 days of life. For a 3 kg neonate, this translates to a 1.67 mg/kg dose, but higher drug exposures are anticipated due to the expected slower metabolism in these younger infants. If the drug exposures following

this single dose are found to be safe, it is planned to administer a single 5 mg dose of DTG to neonates  $\leq 14$  days (Cohort 1B).

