It is unknown the extent to which the DTG exposure will be increased as the enzyme pathways involved in DTG metabolism (UGT1A1 and CYP3A) mature at different rates during early life (30, 31). As expected, the washout elimination of DTG in neonates after *in utero* exposure was slow, with a median elimination half-life of 32.8 hours compared to 12-14 hours in children and adults. In this context, physiologically based pharmacokinetic (PBPK) modelling (32) has been utilized to predict DTG PK and dose optimization in neonates (33). This PBPK model combined existing knowledge on the anatomical, physiological, and metabolic changes (i.e., ontogeny of CYP3A4 and UGT1A1) in neonates with available physicochemical and *in-vitro* data of DTG. This PBPK model was validated using observed clinical data for RAL and midazolam in neonates. Using the final PBPK model, multiple DTG dose strategies were simulated in 100 healthy term virtual neonates (weight ranging from 3.0 to 4.5 kg) with the goal of achieving therapeutic DTG plasma  $AUC_{0-24}$  (50.1  $\mu\text{g}\cdot\text{h}/\text{mL}$ ) and trough concentration (0.99  $\mu\text{g}/\text{mL}$ ) observed in children. **The model predictions indicated that a 5 mg DTG dose may be suitable for term neonates, but any regimen would likely require increased dosing intervals during early life compared to older infants (e.g., every 48 or 72 hours compared to every 24 hours).** The authors' preferred regimen was 5 mg DTG doses every 48 hours from Day 1–20 of life, increasing to 5 mg once daily on Day 21. An important caveat of this PBPK model was the absence of maternal transfer of DTG through the placenta or breast milk. It has been shown that DTG readily crosses the placenta with a reported cord blood to maternal plasma ratio of 1.25 (1.07–1.40) (34). Breastfeeding has been reported to contribute relatively little to infant plasma exposure in the DolPHIN-1 study. The relative infant dose to that of the mother was estimated to be 0.27% (range, 0.13%–0.71%;  $n = 26$ ) (35).

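### The PK precision aim is tied to a prior study's CL/F while the power describes precision around the cohort's own mean, and 86% for n=8 holds under neither at CV 50%

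*Protocol*

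**What the plan says.** Protocol Section 12.1 gives the PK sample-size rationale, and the Synopsis (Section 3) repeats it.

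- Power target: "In each cohort, we aim to achieve at least 80% power".
- Criterion that this target applies to: "95% CI for DTG CL/F that lies within 60% and 140% of the geometric mean estimate of DTG CL/F in a prior relevant study".
- Variability: in the lowest ODYSSEY weight band, "DTG CL/F geometric coefficient of variation (CV%) with the 5 mg dispersible DTG tablet was 33" per cent. Neonates are expected to vary more, with a CV between 30% and 50%, and the calculation is described as "Conservatively assuming that, in each cohort, CV% will be 50" per cent.
- Stated power, with Cohort 1A also at 8 neonates: "8 in Cohort 1B and 24 in Cohort 2 will achieve 86%, 86% and >99% power, respectively". The criterion attached to these figures is worded differently, with no prior study named: "to obtain a 95% CI that lies within 60% and 140% of the geometric mean estimate". The calculation is said to use Student's t-distribution and a published precision method for rich PK sampling.

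Section 12.1 gives no prior CL/F value and no expected ratio of neonatal to prior CL/F. On clearance, Section 8.2.1 reports washout after in utero exposure "with a median elimination half-life of 32.8 hours compared to 12-14 hours in children and adults", and for Cohort 1A says that "higher drug exposures are anticipated due to the expected slower metabolism in these younger infants".

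**The concern.** A 60-140% window around the cohort's own geometric mean asks how precise the estimate is, and n and CV settle the answer. A 60-140% window around a prior study's geometric mean also asks whether neonatal clearance resembles that of the earlier population. That is an equivalence-type criterion, and its power depends on the true ratio of the two clearances. The aim sentence states the second and the power sentence describes the first.

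Two things are at stake. A reader cannot tell which criterion the sample size supports. And the protocol itself expects slower neonatal metabolism, so a window fixed on older children could be missed because clearance is immature, which is what the trial sets out to study, however precise the estimate. The same check shows a further problem: choosing one reading does not by itself rescue the stated power for n=8.

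**Working it through.** **Inputs.** From Section 12.1: n = 8, 8, 24; CV 50% assumed and 33% observed; 95% CI; limits 60% and 140%; t-distribution. From Section 8.2.1: half-lives of 32.8 h against 12-14 h. From Table 2: AUC0-24 of 49.37 µg·h/mL at 5 mg once daily in the 3 to <6 kg band. CL/F is taken as log-normal, with σ² = ln(1 + CV²): 0.2231 at CV 50% and 0.1034 at CV 33%.

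**1. Window around the cohort's own mean.** On the log scale the CI is the mean ± t·s/√n. Because ln 1.4 = 0.3365 is smaller than −ln 0.6 = 0.5108, the upper limit binds. The CI lies inside if t·s/√n ≤ ln 1.4, so

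power = P(χ² with n−1 df ≤ (n−1)·n·(ln 1.4)² / (t²·σ²)).

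| n | CV | t | χ² bound | Power |
|---|---|---|---|---|
| 8 | 33% | 2.365 | 10.97 | 86.0% |
| 8 | 50% | 2.365 | 5.08 | 35.0% |
| 24 | 33% | 2.069 | 141.3 | >99% |
| 24 | 50% | 2.069 | 65.4 | >99% |

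The protocol's 86% is reproduced at CV 33%, not at the stated CV of 50%. Its figure of more than 99% for n=24 is reproduced at both. At CV 50%, n=12 gives 75.7% and n=13 gives 83.8%.

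**2. Window fixed on a prior study's mean.** Let R be the true ratio of neonatal to prior CL/F. Success requires the lower limit ≥ 0.6 and the upper limit ≤ 1.4 times the prior mean. Simulation with 400,000 replicates gives:

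| R | n=8, CV 50% | n=24, CV 50% | n=8, CV 33% | n=24, CV 33% |
|---|---|---|---|---|
| 1.0 | 25% | 92% | 69% | 99.8% |
| 0.8 | 22% | 81-82% | 57% | 99% |
| 0.7 | 10% | 33% | 22% | 61% |
| 0.6 | 2.3% | 2.5% | 2.5% | 2.5% |
| 0.5 | 0.2% | <0.1% | <0.1% | <0.1% |

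The best value for n=8 is at R near √(0.6 × 1.4) = 0.92: about 28% at CV 50% and 78% at CV 33%. So 86% is not reached at any ratio with either CV. At R = 0.6 a larger sample does not help, because a 95% lower limit exceeds the true value only 2.5% of the time at any n.

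**3. Which ratios do the protocol's own figures suggest?** It gives no neonatal CL/F, so these are derived.

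- Half-life, assuming V/F is similar: 12/32.8 = 0.37 to 14/32.8 = 0.43.
- Dosing intervals, taking the modelling target of AUC0-24 = 50.1 as the 24-hour average exposure. The prior CL/F is 5/49.37 = 0.101 L/h. A 5 mg dose every 48 h needs 2.5/50.1 = 0.0499 L/h (ratio 0.49), every 72 h needs 0.0333 L/h (ratio 0.33), and every 24 h needs 0.0998 L/h (ratio 0.99). The cited modelling moves from 48-hourly to daily dosing at day 21.

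Early neonates may therefore sit below 0.5, and infants in the fourth week could be near 1.

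**The case against.** **The intent is recoverable.** The power sentence, its inputs and the named method all point to precision around the cohort's own estimate, and the prior study contributes only a CV. The reference to it in the aim may be a drafting slip. This stands as an account of intent, but the sentence still sets a different criterion in two places.

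**Nothing is decided on it.** A reader might infer that every cohort would be declared to have missed its PK target. The documents do not support that. The 60-140% criterion appears only in the sample-size rationale. Schedule selection and the Cohort 2 interim analysis use C24 and Cmax (Sections 11.4.1 and 11.5), with AUC0-24 as a comparison, and Section 12.2.4 plans no test of CL/F against a prior study.

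**Slower clearance need not mean failure.** A reader might also infer that neonates cannot meet the aim as worded. That holds in effect only at ratios of about 0.6 or below. At 0.8, n=24 still passes with a probability of about 82% (CV 50%) to 99% (CV 33%). The half-life ratio comes from washout after in utero exposure and needs similar V/F. It should not be carried over to Cohort 1A, dosed from day 14, or to the later Cohort 2 samples.

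**Other conventions reach 86% at CV 50%.** Testing against the 60% limit alone gives 86.4% with a normal approximation, or 86.5% with a noncentral t at a one-sided 5% level. Both ignore the 140% limit. The first also departs from the stated t-distribution, and the second from the stated 95% interval. Neither supports the sentence as written.

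**Conclusion.** The inconsistency is real and sits in the text of Sections 3 and 12.1: the aim uses a prior-study window and the power uses an own-mean window. At the stated CV of 50%, the 86% for n=8 is wrong under both. It is 35% around the cohort's own mean, and 25% with a prior-study window at a true ratio of 1, with about 28% the most attainable. For Cohort 2 the figure of more than 99% is right for the own-mean criterion; under the prior-study window it would be 92% at a ratio of 1 and CV 50%.

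Most of the n=8 shortfall therefore comes from the CV, not from the reference study: the own-mean calculation alone drops from 86% to 35% when the CV goes from 33% to 50%. That the 86% was computed at 33% is an inference from the exact match; the protocol does not say so.

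The harm is confined to the sample-size justification and to the precision claimed for Cohorts 1A and 1B. The results assume log-normal CL/F and a t-based interval on the log scale. The low ratios for early neonates also rest on similar V/F, or on reading the dosing intervals as above.

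**What to change.** In Sections 3 and 12.1, remove the words that tie the 60-140% limits to CL/F in a prior study. State that each cohort's 95% CI should lie within 60-140% of that cohort's own geometric mean CL/F, with the prior study supplying only the CV.

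In the same edit, restate the power: for n=8, 86% at CV 33% and about 35% at CV 50%; for n=24, above 99% at both. Say plainly that Cohorts 1A and 1B miss the 80% aim at CV 50%. Removing the prior-study wording alone would leave a wrong power figure in place.

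The cost is a protocol wording change and a less favourable stated power for Cohorts 1A and 1B. Visits, sampling and the analyses in Section 12.2.4 are unaffected. If the sponsor wants to keep 80% power at CV 50% in those cohorts, the calculation gives 13 evaluable neonates in each instead of 8, which is 10 more in total.

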Sample size	
40 evaluable neonates across the two stages: Stage 1, two sequential cohorts - Cohort 1A (n=8) and Cohort 1B (n=8); and Stage 2, Cohort 2 (n=24). In each cohort, we aim to achieve at least 80% power to obtain a 95% CI for DTG CL/F that lies within 60% and 140% of the geometric mean estimate of DTG CL/F in a prior relevant study, per FDA guidance for paediatric PK studies (2). In children in the lowest weight band (3 to <6 kg) of the ODYSSEY trial, DTG CL/F geometric coefficient of variation (CV%) with the 5 mg dispersible DTG tablet was 33%. In neonates, the variability is expected to be higher, with CV% within the range of 30% to 50%. Conservatively assuming that, in each cohort, CV% will be 50%, a sample size of 8 evaluable neonates in Cohort 1A, 8 in Cohort 1B and 24 in Cohort 2 will achieve 86%, 86% and >99% power, respectively, to obtain a 95% CI that lies within 60% and 140% of the geometric mean estimate. These power calculations are based on the Student's t-distribution and apply the methodology described by Wang et al.(3) for rich PK sampling.

Statistical section	
PK analysis: In Stage 1 (Cohort 1A and 1B), a non-compartmental pharmacokinetic analysis will be performed to calculate the subject PK parameters using Phoenix WinNonLin (Certara, USA). Maximum concentration (<math>C_{max}</math>), time to maximum concentration (<math>T_{max}</math>) and last post-dose concentration (<math>C_{last}</math>) will be taken directly from the observed concentration-time data. <math>AUC_{0-all}</math> and <math>AUC_{0-inf}</math> will be determined using the linear-up log-down-trapezoidal method. Cohort 1A and 1B PK data will be pooled for pharmacokinetic modelling and simulation analyses to select the multi-dose schedule for Cohort 2.
 
In Cohort 2, a non-compartmental PK analysis will be performed to calculate the individual subject PK parameters. In addition, a population PK analysis will be performed using all the plasma

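### Sections 3 and 12.1 claim 86% power for the two n=8 cohorts at a 50% CV; the stated method gives 35% there, and 86% only at a 33% CV

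*Protocol*

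**What the plan says.** Section 12.1 (Number of Participants) sets a precision aim for CL/F. The required probability is given first: "In each cohort, we aim to achieve at least 80% power". The event in question is a two-sided interval for clearance inside limits of 60% and 140%, set around the geometric mean from a relevant earlier study. For the ODYSSEY 3 to <6 kg band it reports that "DTG CL/F geometric coefficient of variation (CV%) with the 5 mg dispersible DTG tablet was 33" per cent. For neonates, "the variability is expected to be higher, with CV% within the range of 30% to 50" per cent. It then fixes the planning value: "Conservatively assuming that, in each cohort, CV% will be 50%, a sample size of 8 evaluable neonates in Cohort 1A". Cohort 1B has the same size and Cohort 2 is three times as large. The power claimed for the three cohorts, in that order, reads: "will achieve 86%, 86% and >99% power, respectively, to obtain a 95% CI that lies within 60% and 140% of the geometric mean estimate". The calculations are said to rest on Student's t-distribution, using a published method for rich PK sampling.

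The Sample size row of the Section 3 synopsis carries the same assumption ("Conservatively assuming that, in each cohort, CV% will be 50" per cent) and the same three power figures.

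**The concern.** The paragraph contains two CVs, 33% from the earlier trial and 50% for planning, and attaches the power to the second. Eight participants are very few for a 95% CI to stay below 140% of its point estimate when the CV is 50%, so 86% looks too high.

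PK is a primary objective, and Section 12.2.4 reports geometric means with 95% CIs separately for Cohorts 1A and 1B. Ethics, regulatory and DSMB readers are told that each of these cohorts will estimate clearance to the stated precision with high probability, even at the top of the expected range of variability. If 86% belongs to the 33% CV, that assurance is false for Stage 1 and the protocol does not meet its own aim.

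**Working it through.** **Inputs, all from Section 12.1.** Two-sided 95% CI; limits 60% and 140% of the geometric mean; n = 8, 8 and 24; planning CV 50%; prior-trial CV 33%; Student's t. The log scale is inferred from the geometric mean and geometric CV; the text does not state it.

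**Criterion.** For a log-normal parameter, σ = √ln(1 + CV²). The CI on the log scale is the mean ± t(0.975, n−1)·s/√n. The 140% limit binds, because ln 1.4 = 0.3365 is smaller than −ln 0.6 = 0.5108. The requirement is therefore s ≤ s_max, where s_max = ln 1.4 · √n / t(0.975, n−1), and

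power = P(χ² with n−1 df ≤ (n−1)·(s_max/σ)²).

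**Reproducing the stated figures.** For n=8, t = 2.3646, so s_max = 0.3365 × 2.8284 / 2.3646 = 0.4025.

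- CV 33%: σ = 0.3215; 7 × (0.4025/0.3215)² = 10.97; power = 86.0%. This is the printed figure. Solving for 86% at n=8 returns a CV of 33.0%.
- CV 50%: σ = 0.4724; 7 × (0.4025/0.4724)² = 5.08; power = 35.0%.

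For n=24, t = 2.0687 and s_max = 0.7968. At CV 50%, 23 × (0.7968/0.4724)² = 65.4, and power is above 99.9%. The Cohort 2 statement is reproduced at the stated 50%.

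**Power at n=8 across the protocol's own range.**

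| CV | Power |
|---|---|
| 30% | 93% |
| 33% | 86% |
| 35% | 80% |
| 40% | 63% |
| 45% | 48% |
| 50% | 35% |

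At CV 50%, if the sample SD equals σ, the log half-width is 2.3646 × 0.4724/√8 = 0.395. The CI then runs from 67% to 148% of the geometric mean, already past the upper limit. For scale, at CV 50% n=12 gives 75.7% and n=13 gives 83.8%.

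**Other ways to reach 86% at CV 50%, n=8.** Student-t variants give:

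- σ set equal to CV: 28%
- arithmetic ±40%: 51% (59% with the log-scale SD)
- 90% CI: 66%
- total CI width: 67%
- noncentral t: 38% to 75%
- 60% limit only: 89% (84% with σ = CV)

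None is within 2 points of 86%. A normal approximation with known SD and only the 60% limit gives 86.4%, but it contradicts the stated t method and ignores the stated 140% limit.

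**Limits fixed around an earlier study's mean.** Section 12.1 first words the target this way. If the true mean equals that reference, simulation at CV 50% gives about 25% for n=8 and about 92% for n=24.

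**The case against.** The strongest defence is that the method paper is not reproduced in the protocol and the log scale is inferred, so the sponsor may have used another criterion. That is why the origin of the 86% should be called apparent and not established. It does not rescue the figure: no Student-t variant that was tried gives 86% at CV 50%, while one criterion yields both the Cohort 2 figure at 50% and exactly 86% at the other CV in the paragraph.

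A second defence is that no decision rule uses CL/F precision. Sections 11.4.1 and 12.2.4 choose the Cohort 2 schedule from simulated C24 and Cmax, with DSMB agreement. This stands. A reader might infer that schedule selection is undermined or that the cohorts must be enlarged; the documents do not support either from this error alone. Nor is poor precision certain, since power is still 80% or more if the CV is at or below about 35%.

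A reader might also infer that 50% is not conservative at all. Table 2 in Section 8.2 gives an AUC CV of 49% in the 3 to <6 kg band on a fixed 5 mg dose, and with dose fixed CL/F has the same geometric CV. But 50% still exceeds 49% and is the top of the protocol's range. The 49% comes from combined trials with n=8 and need not agree with the ODYSSEY-only 33%. The fair statement is that 50% leaves little margin, given that neonates are expected to vary more.

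Finally, it is tempting to let the 16 pooled Stage 1 infants carry the target, since n=16 at CV 50% gives 97%. That holds only if both age cohorts share one mean CL/F, whereas Section 8.2.1 describes enzyme pathways that mature during early life. With a within-cohort CV of 50%, simulated pooled power is about 90% at a 1.5-fold difference in mean CL/F and 69% at a 2-fold difference. Both ratios are assumptions; the documents give none.

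**Conclusion.** Wrong as written. At the stated CV of 50% the power in Cohorts 1A and 1B is 35%, which is 51 points below the printed 86% and 45 below the 80% aim. The printed figure matches a CV of 33% and appears to have been computed there. The Cohort 2 figure stands when the limits are set around the cohort's own estimate, and is about 92% if they are fixed around an earlier study's mean that equals the true mean.

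The conclusion rests on log-normal CL/F, σ = √ln(1 + CV²), all planned participants evaluable, and both the 60% and 140% limits applied. The error is confined to the two cohorts of 8. It does not show that the trial is too small for its purpose.

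**What to change.** In Section 12.1 and in the Sample size row of Section 3:

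- Restate the power for n=8 as 35% at CV 50% and 86% at CV 33%, adding that 80% is kept only up to a CV of about 35%. Keep more than 99% for n=24.
- Remove, or reconcile with these figures, the claim that each cohort reaches at least 80% under a conservative CV. Note that 50% leaves little margin over the 49% in Table 2.
- Do not insert a pooled n=16 figure of 97%. Leave it to the sponsor to say why Stage 1 has 8 per cohort: the protocol does not state that this size was chosen for model-based schedule selection, and the correction should not supply that reason.

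The cost is a wording amendment in two places and a less favourable stated power. No change in sample size, procedures or analysis is needed to correct the figure.

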## 12.2. Statistical Analysis Plan

### 12.2.1. Planned Analyses

Planned interim analyses for futility based on safety and/or PK data will be conducted after the last participant completes follow up in Cohorts 1A and 1B, respectively, and after 50% of participants have completed follow up in Cohort 2; or early termination of the study. The final analysis will be conducted after all participants complete the study; or early termination of the study.

